8.4.1.1. Pregnancy

Whenever the site is notified of a possible pregnancy, the patient should be asked to come in for an unscheduled visit to perform a serum pregnancy test. If a female patient becomes pregnant, the patient must stop taking investigational product immediately and be withdrawn from the study. The patient must be followed by the Investigator through pregnancy outcome. The mother (and infant) will be followed as considered appropriate by the Investigator and the Medical Monitor. For reporting purposes, pregnancy is not considered an AE (see [Section 13.1.10](#)).

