- i New investigational product bottles will be dispensed if the patient is up-titrated. Unless up-titrated, patients are expected to use up each investigational product bottle before a new bottle will be dispensed. No new bottles will be dispensed if dose frequency is changed. Patients will be instructed to begin dosing on Day 1, after completing all study assessments. Patients will be instructed to take investigational product at approximately the same time of day. Patients must be instructed to swallow the tablet whole; they must not chew, divide, or crush the tablet.
- j Dose titration of investigational product may occur starting after the Week 12 Visit, or any study visit thereafter for patients on all dosing regimens, based on CP score, tolerability, and safety laboratory tests from the previous visit. Subsequent dose titration(s) may occur no earlier than 6 weeks after the previous dose titration and will be based on tolerability and CP score.
- k Urine β -hCG pregnancy tests must be performed in females of childbearing potential prior to entry and at every visit (except Week 3). If positive, a confirmatory blood test must be performed at the central laboratory. If the confirmatory blood test is also positive, the patient may not continue in the study. (Additional testing may be conducted where required, regionally).
- l The patient will be given the option to return to the clinic the following morning for the 24-hour postdose sample or samples can be obtained by a home health care designee. Patients who are discontinued from investigational product prior to completion of the study are encouraged to continue to follow the regular visit schedule, with the exception of PK sampling.
- m The noninvasive radiological liver fibrosis measurement devices (such as, FibroScan® device [Echosens; Paris, France]) will be used at all study sites to collect hepatic stiffness measurements.
- n Patients will complete a TE/ELF and ultrasound assessment, every 6 months (± 2 weeks) after Week 48.
- o ECG and urine dipstick will be done yearly (± 2 weeks) after Week 48 Visit.
- p Ultrasound will be conducted to enhance HCC surveillance. For all on study (eg, post-Day 0) ultrasounds: Unless HCC has already been confirmed by biopsy, a second confirmatory image (eg, MRI) should be obtained to confirm suspected HCC.

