8.4.1.3. Pregnancy

If a female patient becomes pregnant, she must interrupt treatment with investigational product immediately, but should continue with the study visit schedule. As described in [Section 13.1.9](#) pregnancy is not considered an AE for reporting purposes. The patient may restart investigational product when she is no longer pregnant or breastfeeding (if applicable) at the discretion of the Investigator and after discussion with the Medical Monitor as described in [Section 13.1.9](#)). New baseline procedures should include pregnancy testing.

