8.4.4. Patient Discontinuation Notification

The Investigator must notify the Sponsor as soon as possible if any patient prematurely discontinues from the study. The date when the patient is withdrawn and the primary reason(s) for discontinuation must be recorded in the eCRF; additional information may be requested by the Sponsor to complete a discontinuation narrative. This information must be documented in the eCRF.

If a patient is withdrawn from the study early (regardless of the cause), all of the early termination (ET)/EOS evaluations are to be performed at the time of withdrawal, to the extent possible.

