9.7.5. Day 1 Procedures (Randomization)

- Verify that the patient has fasted for at least 8 hours.
 - Record fasting status in the source and eCRF
 - If the patient reports having eaten within 8 hours, document accordingly in the source and eCRF and remind the patient that fasting is required prior to all study visits.
- Review inclusion and exclusion criteria for eligibility.
- Perform a physical examination.

- Review and record any non-study related medical or surgical treatment procedures and any medically relevant health care professional (HCP) or non-HCP related office visits that have occurred since the previous study visit.
- Assess and record vital signs and weight (oral temperature, sitting heart rate, respiratory rate, and sitting blood pressure).
- Assess and record any pretreatment-emergent AEs.
- Review and record prior concomitant medications.
- Perform assessments for calculation of CP Score ([Section 14.1.1](#)).
- Administer Quality of Life and Patient questionnaires ([Section 13.2.6](#)).
- Randomize the patient only if s/he meets all inclusion criteria and no exclusion criteria.
- Record the visit in IWRS and dispense investigational product
 - Instruct the patient to begin dosing on the day of the Day 1 Visit.
- Obtain urine sample for urinalysis (dipstick).
- Perform a urine-based β -hCG pregnancy test in females of childbearing potential.
- Obtain blood samples for
 - Serum chemistry, hematology, and coagulation
 - Markers of inflammation and fibrosis (IL-6, hs-CRP, TNF- α , IgM, IgG, IgA, CK-18-M30, ELF [HA, P3NP, and TIMP 1])
 - Fasting PK assessment
 - Bile Acid/C4/FGF-19
- Perform TE using the Fibroscan® TE device. If the TE cannot be performed on Day 1 (eg, device/technician unavailability, scheduling issues, TE data is needed to inform cirrhosis assessment, etc.), the procedure may be completed within the Day 1 Visit window, (if data is needed for cirrhosis assessment) or as close as possible to the Day 1 Visit, preferably, after patient eligibility has been confirmed. Instruct the patient to take Day 1 dose on the day of this visit.
- Schedule the next visit, reiterate dosing instructions, and advise the patient:
 - NOT to take investigational product on the morning of the next visit, and
 - To bring the investigational product bottle(s); s/he will dose at the clinic (if this is in compliance with the established dosing frequency), and

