13.1.9. Pregnancy and Follow-Up

Pregnancies are not considered AEs in and of themselves; however, if a female study participant becomes pregnant while she is enrolled in the clinical study, she must interrupt treatment with investigational product immediately (see [Section 8.4.1.3](#)) and the Sponsor must be notified within 24 hours of the Investigator’s awareness of the pregnancy by completing the Pregnancy CRF in the EDC system and downloading and completing the Pregnancy Report Form. The Pregnancy Report Form must be emailed to PPD [REDACTED] or faxed to PPD [REDACTED]. The patient and neonate must be followed for outcome information and/or as considered appropriate by the Investigator and Sponsor.

The patient may restart investigational product when she is no longer pregnant or breastfeeding (if applicable) at the discretion of the Investigator and after discussion with the Medical Monitor. The patient must have a negative pregnancy test before restarting investigational product. If a patient’s pregnancy is terminated early (planned or unplanned), she must have termination of the pregnancy confirmed by a serum β -hCG test before restarting investigational product.

Completing the Pregnancy Report Form is not a substitute for reporting an AE/SAE when and AE/SAE has occurred. In the situation when an AE/SAE has occurred, the AE/SAE reporting procedures described in [Section 13.1.4](#) must also be followed.

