Hematology	Hemoglobin, hematocrit, white blood count with differential, neutrophils, lymphocytes, monocytes, eosinophils, basophils, platelets, red blood cell count (including MCV, MCH, MCHC)
Coagulation	PT, PTT, INR
Urinalysis (dipstick)	pH, specific gravity, total protein, glucose, ketones, bilirubin, blood, microscopic exam, urobilinogen, albumin, creatine, leucocytes, nitrates, albumin/creatinine ratio (if positive), pregnancy
Markers of Inflammation	IL-6, hs-CRP, TNF- α , IgM, IgA, IgG, CK-18-M30
Noninvasive measurements of liver fibrosis, liver stiffness and cirrhosis	ELF (HA, P3NP, and TIMP-1) TE
PK assessments	OCA (parent and conjugates [glyco and tauro], metabolite OCA-glucuronide)
PD markers	C4, FGF-19 and plasma bile acids

ALP = alkaline phosphatase; ALT = alanine aminotransferase; AST = aspartate aminotransferase; C4 = 7 α -hydroxy-4-cholesten-3-one; CK-18-M30 = cytokeratin-18 neopeptide M30; CP = Child-Pugh; CPK = creatine phosphokinase; ECG = electrocardiogram; ELF = enhanced liver fibrosis; FGF-19 = fibroblast growth factor-19; GGT = gamma-glutamyl transferase; HA = hyaluronic acid; HDL = high density lipoprotein; hs-CRP = high-sensitivity C-reactive protein; IgA = immunoglobulin A; IgG = immunoglobulin G; IgM = immunoglobulin M; IL-6 = Interleukin 6; INR = international normalized ratio; LGL = low-density lipoprotein; MCH = mean corpuscular hemoglobin; MCHC = mean corpuscular hemoglobin concentration; MCV = mean corpuscular volume; OCA = obeticholic acid; PBC = primary biliary cirrhosis; P3NP = procollagen 3 N-terminal peptide; PT = Prothrombin time; PTT = partial thromboplastin time; SGOT = Serum glutamic oxaloacetic transaminase; SGPT = serum glutamic-pyruvic transaminase; TE = Transient Elastography; TG = triglyceride; TFT = thyroid function test; TIMP-1 = tissue inhibitor of metalloproteinase 1; TNF- α = tumor necrosis factor- α ; VLDL = very-low density lipoprotein

Laboratory reference ranges for the study will be based on the laboratory vendor range.

Urine based β -hCG pregnancy tests will be performed in female patients of childbearing potential per protocol specified visits (see [Table 1](#)). If a urine pregnancy test is positive, a serum pregnancy test must be performed to confirm the result. If positive, the Sponsor must be notified and the patient will be followed as outlined in [Section 13.1.9](#) until pregnancy outcome.

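### Table 1 footnote k removes a patient with a confirmed positive pregnancy test from the study at any tested visit, while 8.4.1.3 keeps a pregnant patient on the visit schedule with product interrupted

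*Protocol*

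**What the plan says.** All references are to Version 2 of the protocol unless stated otherwise.

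- **Section 7.1.2, Table 1, footnote k.** Women of childbearing potential have a urine test before entry and at each visit other than Week 3. A positive result is confirmed on blood at the central laboratory. Then: "If the confirmatory blood test is also positive, the patient may not continue in the study".
- **Section 8.4.1.3, Pregnancy.** If a patient becomes pregnant, "she must interrupt treatment with investigational product immediately, but should continue with the study visit schedule". She may later restart product once pregnancy and any breastfeeding have ended, at the investigator's discretion and after discussion with the Medical Monitor.
- **Section 13.1.9, Pregnancy and Follow-Up.** Repeats the interruption and sets conditions for restart: "The patient must have a negative pregnancy test before restarting investigational product".
- **Section 13.2.5, Laboratory Assessments.** After serum confirmation: "If positive, the Sponsor must be notified and the patient will be followed as outlined in" Section 13.1.9.
- **Section 9.7.13, Table 4.** The pregnancy row gives product status as discontinued and points to either the Early Termination or the Treatment Discontinuation scenario.

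**The concern.** The footnote is not limited to tests before entry, so it also governs positives in patients who have already taken product. For them it gives the opposite instruction to the dedicated pregnancy section. The schedule is where sites look up the test, so a site could reasonably act on the footnote. That would end scheduled laboratory, Child-Pugh, MELD and clinical-event follow-up of an exposed patient with moderate or severe hepatic impairment, and would rule out the restart that two other sections allow. Safety is one of the two primary objectives in a trial of about 50 patients, so a rule on whether an exposed patient stays under observation should read the same way throughout.

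**Working it through.** No power, alpha or sample size figure is involved. The check is a count of the tests that the footnote governs and a comparison of the relevant sections.

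**1. Which tests the footnote covers.** The Table 1 pregnancy row has tests at Screening, Day 1 and Weeks 6, 12, 18, 24, 30, 36 and 48, which is 9 tests through Week 48. Two of these, Screening and Day 1, come at or before entry; footnote i says "Patients will be instructed to begin dosing on Day 1, after completing all study assessments", so the Day 1 sample precedes the first dose. That leaves 9 − 2 = 7 later tests through Week 48. Section 9.7.12 adds one at each 3-monthly visit after that. The footnote's sentence therefore applies mostly to tests in dosed patients.

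**2. The two rules for a dosed patient with a confirmed positive.**

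| Question | Footnote k | 8.4.1.3 and 13.1.9 |
|---|---|---|
| Does she stay in the study? | No | Yes, on the visit schedule (8.4.1.3) |
| What happens to product? | Ends with participation | Interrupted |
| Can she restart? | No | Yes, under stated conditions (both) |

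**3. Which rule is likely intended.** Sections 8.4.1.3 and 13.1.9 agree on interruption and restart. Section 13.2.5 directs a confirmed positive to 13.1.9. Section 8.4.2 makes only liver transplant a mandatory reason to discontinue product, and 8.4.3 does not list pregnancy. Apart from withdrawal of consent, the reasons in 8.4.3 leave the patient in the study. Footnote k stands alone.

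**4. Table 4.** The pregnancy row's discontinued status does not match the interruption in 8.4.1.3 and 13.1.9. Both scenarios to which the row refers also show product as discontinued, and the text of 9.7.13 ties the EOT visit to discontinuation. Version 2 of the table has no interruption row, although the text of 9.7.13 does provide for a patient who interrupts product, stays on scheduled visits and has her EOS visit last.

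**5. What is kept under either rule.** On early withdrawal, "all of the early termination (ET)/EOS evaluations are to be performed at the time of withdrawal" as far as possible (8.4.4), although 9.7.13 does not count a missed EOT or EOS visit as a deviation. SAEs within 30 days of leaving the study are reported (13.1.7). Ongoing related or clinically significant adverse events and possible drug-induced liver injury are followed (13.1.8), as is pregnancy outcome (13.1.9, 13.2.5).

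**The case against.** The best counter-argument is that the document largely settles the matter itself. The dedicated section, the follow-up section and the laboratory section point the same way, and footnote l encourages patients taken off product to keep their visits. On this view footnote k is an eligibility rule with one loosely worded sentence. This stands as a reason for low severity. It does not remove the conflict: the footnote names every visit except Week 3, and not continuing in the study describes someone already in it.

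A reader might go further in three ways that the documents do not support.

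- **That the sentence is proven to be a leftover from Version 1.** Version 1 carried the same sentence, and there it matched a rule that "the patient must stop taking investigational product immediately and be withdrawn from the study". But Version 2 edited this footnote, adding the Week 3 exception, and kept the sentence. A leftover is plausible, not established, and the finding does not need it.
- **That Day 1 procedures allow randomization ahead of the pregnancy test.** Section 9.7.5 lists "Randomize the patient only if s/he meets all inclusion criteria and no exclusion criteria" and dispensing before the test, but list order is not a stated sequence, and footnote i puts dosing after all assessments. No error is shown. A mandatory hold for central confirmation could also run into the 28-day screening limit.
- **That substantial follow-up is lost.** The event is unlikely, the visits at stake would be off product, and the main safety outcomes are covered in either case.

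**Conclusion.** The contradiction is real for any patient with a confirmed positive after the first dose: footnote k ends participation, while 8.4.1.3 continues it and, with 13.1.9, allows restart. For samples taken before the first dose the footnote is sound and useful, because Section 8.3 does not list pregnancy as an exclusion criterion.

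Severity is minor. Probably 0 or 1 patient is affected. This is a judgment from the typical age at diagnosis of 40 to 70 years (5.1), the contraception requirement (8.2) and the planned size of about 50; the protocol gives no pregnancy rate. No endpoint, analysis or sample size depends on the point. That 8.4.1.3 and 13.1.9 state the intended rule is an inference from their agreement with each other and with 13.2.5, 8.4.2 and 8.4.3, and the sponsor should confirm it.

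**What to change.** 1. **Footnote k.** Keep the testing requirement. Limit the exclusion to a confirmed positive on a sample taken before the first dose (Screening or Day 1). For a confirmed positive on a later sample, refer to 8.4.1.3 and 13.1.9. Do not delete the sentence, since it is the explicit text that keeps a pregnant patient out before dosing.
2. **Table 4, pregnancy row.** Replace the whole row: product interrupted, regular visit schedule, EOS at the final study visit, with Early Termination used only if consent is withdrawn. Changing the product-status cell alone would leave the row pointing to two scenarios that still show product as discontinued.

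The cost is one footnote and one table row, with no added test or visit and no change to sample size or analysis.

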7.1.3. Study Duration

Patients will receive double-blind treatment for at least 48 weeks. Patients who have completed their 48-week double blind treatment period will continue double-blind treatment until all randomized patients have completed their 48-week treatment period and the database for that period is locked (approximately 3 years). Patients will then be given the option to go on open-label treatment.

7.2. Number of Patients

Approximately 50 patients will be enrolled in this study.

7.3. Planned Dosing Regimen

All patients will initiate investigational product once weekly with OCA 5 mg or matching placebo (Table 2). Titration may be considered as early as the Week 12 Visit. Following visit procedures at Week 12, if the investigational product is tolerated and laboratory assessments do not indicate a safety concern, the patient may up-titrate to OCA 5 mg twice weekly and may start the higher dose regimen no earlier than 2 days after they took their last dose. Dosing will then occur at least 3 days apart. Every 6 weeks thereafter, based on safety and tolerability assessments, patients can be considered for further up titration as described below (Table 2). At each titration visit, the patient may start the higher dose regimen no earlier than 2 days after the prior dose.

Patients with CP-B may titrate to a maximum dose of OCA 5 mg once daily.

Patients with CP-C may titrate to a maximum dose of OCA 10 mg twice weekly at least 3 days apart.

If, during the course of the study, a patient transitions from CP- B to CP-C, or vice versa, the maximal dose for the new CP classification would apply (Table 3).

Table 2: Planned OCA or Matching Placebo Dosing Regimen by Child-Pugh Score

	Child-Pugh B (Moderate Hepatic Impairment)		Child-Pugh C (Severe Hepatic Impairment)	
	Treatment Group		Treatment Group	
	OCA	Placebo	OCA	Placebo
Starting Dose (Day 1)	5 mg once weekly	matching placebo	5 mg once weekly	matching placebo
Titration 1^a	5 mg twice weekly ^b	matching placebo	5 mg twice weekly ^b	matching placebo
Titration 2^a	10 mg twice weekly ^b	matching placebo	10 mg twice weekly ^b	matching placebo
Titration 3^a	5 mg once daily	matching placebo	NA	NA

^a Planned titration regimen is shown; however, the titration of dose and/or frequency is dependent on patient tolerability and/or changes in Child-Pugh Score at any time during the study.

^b Dosing per the twice weekly schedule must be at least 3 days apart.

7.4. Dose Adjustment Criteria

Dose titration may follow the scheduled dosing regimens described in [Section 7.3](#) or occur due to tolerability concerns or as a result of changes in a patient's CP Score.

Dose titrations may involve increases or decreases in dosing frequency and are dependent on tolerability (as assessed by a review of AEs and safety laboratory results). In general, down-titration may be done in response to tolerability concerns and can occur at any time. Up-titration will be done per protocol based on tolerability, as assessed by the Investigator based on response, or following resolution of a tolerability concern that previously led to down-titration. Up-titrations may only occur to the maximum dose and frequency indicated for each dosing regimen as defined in [Section 7.3](#).

Scheduled Dose Titration - After initiation of OCA or matching placebo, titration may be considered as early as the Week 12 Visit. Subsequent titrations in dose or dosing frequency for patients may occur no earlier than 6 weeks following an up-titration.

Tolerability Dose Titration - Investigators may decrease the dosing frequency or dose as considered clinically appropriate (eg, tolerability)

Dose Titration due to Change in CP Score – Over the course of the study, a patient's CP category may change. When a patient demonstrates a change in CP category (as assessed per [Table 10](#)), dosing should be reassessed and modified if appropriate ([Table 2](#)). Changes to the dosing regimen are not mandatory and should be based on clinical judgment and change in CP score. The titration steps for CP-B and CP-C patients are identical with exception of the maximum allowed dose. Therefore, if a patient changes CP class from B to C, or vice versa, the maximal dose for the new regimen will apply ([Table 3](#)). If a patient improves to CP-A during the study, the maximal CP-B dose will still apply. If a patient has not yet reached the maximal dose, the appropriate titration regimen ([Table 2](#)) should be followed.

Table 3: Maximum Daily dose based on change in Child-Pugh Category

Original Status	New Status ^a		
	Child-Pugh A	Child-Pugh B	Child-Pugh C
Child-Pugh B	No change	No change	10 mg twice weekly
Child-Pugh C	5 mg once daily	5 mg once daily	No change

^a Once a patient begins dosing with the new dosing regimen, titration should occur as described for that dosing regimen in [Section 7.3](#).

^b Dosing per the twice weekly schedule must be at least 3 days apart.

CP Scores will be calculated at all study visits (except Week 3). While PBC-specific versions of CP scores are available, this study will use the standard calculation ([Pugh 1973](#), [Lucey 1997](#)). All associated visit data (including central laboratory results) should be entered into the electronic case report form (eCRF) in a timely fashion to confirm that the patient's CP Score has

not changed. If a change in CP Score is observed independent of a study visit, the patient should be contacted via phone to discuss the need for a dosing modification and should be asked to return to the investigative site as soon as possible if a new bottle of investigational product is required to be dispensed.

